A recent publication by Morretti et al [4] evaluated the effect of different doses of oral iron in non-pregnant iron deficient young women. They evaluated the effect of varying doses of daily ferrous sulfate and once and twice daily dosing of ferrous sulfate on hepcidin levels and fractional and total iron absorption. Women were treated with a single daily dose ranging from 40-240mg of elemental iron. This 6-fold increase in elemental iron dosage only resulted in a 3 fold increase in the amount of elemental iron absorbed, contradicting the notion that more iron is better. In a second arm of the study, women were treated with twice daily dosing for a total of 180mg of elemental iron. **The results of the study demonstrated that 24 hours after a dose > 60mg, hepcidin increased and fractional iron absorption decreased by 35-45%. Multiple daily doses did not increase iron absorption beyond single daily dosing.** The authors concluded that providing daily dosages less than 80mg of elemental iron and avoiding

twice daily dosing maximized iron absorption. **The results of the study by Morretti et al challenge the conventional wisdom that more severe iron deficiency anemia in pregnancy is best treated by increasing from daily to twice daily supplementation. Morretti et al also did not evaluate for gastrointestinal side effects or increase in hemoglobin.**

Given the high incidence of iron deficiency anemia in pregnancy and the associated complications, we propose a prospective, randomized double blinded clinical trial to evaluate the optimal dosing of oral iron supplementation in pregnancy. We will recruit mothers identified as having iron deficiency anemia at the time of routine prenatal blood work in the second trimester. These subjects will be randomized to daily or twice daily ferrous sulfate 325mg (65mg of elemental iron). The primary outcomes will be hemoglobin concentration at the time of admission for delivery and post-partum and assessment of gastrointestinal side effects. The secondary outcome will be frequency of blood transfusion at the time of delivery.

Hypothesis: Once daily dosing of ferrous sulfate 325mg/dL will be associated with increased maternal hemoglobin concentration at the time of delivery and post-partum and decreased gastrointestinal side effects.

Specific Aims

1. Determine whether once daily dosing of oral iron is more effective in raising maternal Hgb concentration than twice daily dosing.

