In addition to routine standard of care blood draws, subjects will have two extra samples of blood taken for research use at no cost to them. The first will be drawn at the time of enrollment, generally at the time of a clinically indicated blood draw for routine prenatal labs. The second will be drawn at the time of admission to the hospital for delivery or on post partum day 1, again generally at the time of an otherwise clinically indicated blood draw. At this time, a separate tube of about 10mL will be drawn for research purposes only. A sample of cord blood from the placenta will be obtained following delivery of the neonate as well. These samples will be stored for analysis of hepcidin and ferritin at the conclusion of the study. These values will be for research use only and will not be used in clinical care.

Subjects will be administered a validated questionnaire regarding gastrointestinal (GI) symptoms of iron usage at the time of follow up clinic visits [5]. This questionnaire will be administered via RedCap or via paper per patient preference. Compliance will be monitored by having the patient bring pill packs to her clinic visits.

Whether or not the patient required a blood transfusion in the peripartum period will be recorded. Due to the relative infrequency of this outcome, this will be evaluated as a planned secondary outcome with the understanding that the trial will not be powered specifically for this outcome.

All samples collected will be collected for, stored, and processed by the MU Biorepository. Following study related analysis, the MU Biorepository will de-identify what is left of the samples and store the excess for future non-specified research endeavors.

Risks and Benefits

1. Iron therapy is associated with mild gastrointestinal symptoms (upset stomach and diarrhea). Increased iron dosage may be associated with an increased risk of these symptoms. Significant gastrointestinal symptoms are rare with once or twice daily iron dosage. The additional iron in maternal diet (which is classically iron poor in the US) or in prenatal vitamins will not pose any additional maternal risk. There is no fetal risk to this study.
2. There are no individual benefits to enrollment in the study.

Subject withdrawal criteria and procedures specifying

- When and how to withdraw subjects from the trial / investigational product treatment.
If subjects are not compliant with the tasks required in the protocol.

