- The type and timing of the data to be collected for withdrawn subjects.
All data collected from a withdrawn subject will immediately be destroyed.
- Whether and how subjects are to be replaced.
To replace withdrawn subjects, we will recruit another pregnant mother
- The follow-up for subjects withdrawn from investigational product treatment/trial treatment.
There will be no follow-up.

Data handling:

All data will be coded with an ID number. The key containing the ID numbers will be kept in a locked file separate from the data. Data generated from samples tested for this study will be stored by the MU Biorepository and by the research staff. . The data will be kept for 7 years after study completion. This data will not be shared with outside investigators or used for research other than this study. Additionally, data from this study will be included in the Prospective Obstetric Database (PODS) study for future use in de-identified fashion.

Data Analysis

Statistical Analysis: Statistical analyses will be performed using the IBM SPSS statistical software version 22 (IBM Corporation, Armonk, NY, USA). ANOVA will be used to assess the difference in mean hemoglobin at the time of admission and post-partum in the three arms for the study. Regression analysis will be used to explore the relationships of iron supplementation on maternal hemoglobin at delivery and fetal hemoglobin, hepcidin, and ferritin while controlling for maternal ferritin and hepcidin at enrollment. A planned secondary analysis will be to use a Chi-square or Fisher's exact test as appropriate to examine the incidence of blood transfusion during the admission for delivery. Significance will be set at $P \leq 0.05$.

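### Women withdrawn for non-compliance have all their data destroyed and are replaced without follow-up, so a primary comparison can be selected on its own outcome

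*Combined protocol and SAP*

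**What the plan says.** The section on subject withdrawal gives one reason for withdrawal: "If subjects are not compliant with the tasks required in the protocol". It sets no threshold and does not list the tasks. Study Design says: "Compliance will be monitored by having the patient bring pill packs to her clinic visits". Pill-taking is therefore one plausible task; clinic visits and questionnaires could be others.

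The consequences of withdrawal are stated without exception:

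- Data: "All data collected from a withdrawn subject will immediately be destroyed".
- Replacement: "To replace withdrawn subjects, we will recruit another pregnant mother".
- Follow-up: "There will be no follow-up".

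The Summary states: "The primary outcomes will be hemoglobin concentration at the time of admission for delivery and post-partum and assessment of gastrointestinal side effects". Risks and Benefits describes the GI symptoms of iron as mild and says "Increased iron dosage may be associated with an increased risk of these symptoms", but also "Significant gastrointestinal symptoms are rare with once or twice daily iron dosage".

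The Data Analysis section names no analysis set, no missing-data method and no report of withdrawals by arm. The Power Analysis paragraph enrols until 50 women are randomised and also allows for drop-out and replacement. Women lost because they deliver elsewhere or transfer care are mentioned only there. They are a separate group, and nothing in the plan destroys their data.

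**The concern.** Withdrawal is decided after randomisation, on behaviour that treatment can influence. A woman who stops her pills because of GI symptoms can be judged non-compliant, and her symptom questionnaires are then destroyed. If this happens at different rates in symptomatic and asymptomatic women, the remaining groups no longer give a fair comparison of GI effects. Specific Aim 2, which asks whether once-daily dosing has fewer side effects, rests on that comparison.

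Replacement restores the number of women but not the randomised comparison. The destroyed scores cannot be recovered, so a later analysis plan cannot repair the loss. Counts by arm might be rebuilt from the pharmacy's allocation list, but the plan does not provide for this, and the reasons for withdrawal may be lost. It is also unclear whether withdrawn women count toward the 50.

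**Working it through.** **The plan's own figure.** Inputs from the Power Analysis paragraph are a difference of 1 unit (mg/dL as printed), SD 1, alpha 0.05 (two-sided assumed) and 80% power. The exact two-sample t-test gives 78.1% power at 16 per arm and 80.7% at 17, so the stated 17 per arm is reproduced. With 25 randomised per arm and 20% loss, 25 × 0.80 = 20 remain and power is 86.9%. Replacement is therefore not needed for power at the stated loss.

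**GI outcome.** The documents give no symptom or withdrawal rates and no yes/no definition, so every rate below is an assumption. Let p be the true symptom rate in an arm, q the share of symptomatic women deleted and a the share of asymptomatic women deleted. Among the women who remain:

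observed rate = p(1 − q) / [p(1 − q) + (1 − p)(1 − a)]

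Worked example with p = 0.20 and 0.40, q = 0.50, a = 0:

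- once daily: 0.10 / (0.10 + 0.80) = 0.111
- twice daily: 0.20 / (0.20 + 0.60) = 0.250
- difference: 13.9 points instead of 20

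*Case A: a = 0, same q in both arms. Entries are the observed difference in points.*

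| True rates (once vs twice daily) | True difference | q = 10% | 25% | 50% | 75% |
|---|---|---|---|---|---|
| 5% vs 10% | 5 | 4.6 | 3.9 | 2.7 | 1.4 |
| 20% vs 40% | 20 | 19.1 | 17.5 | 13.9 | 8.4 |
| 60% vs 80% | 20 | 20.8 | 22.1 | 23.8 | 22.7 |

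In Case A the difference grows only if p1 + p2 − 1 > p1·p2·q. For 60% vs 80% this means q < 0.40/0.48 = 0.83. For 20% vs 40% it never holds.

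*Case B: unequal q, a = 0, 20% vs 40%.*

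- q = 25% once daily and 50% twice daily: 0.158 vs 0.250, or 9.2 points.
- q = 50% once daily and 25% twice daily: 0.111 vs 0.333, or 22.2 points.

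*Case C: asymptomatic women also deleted, 20% vs 40%, same shares in both arms.*

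- q = 25%, a = 10%: 0.172 vs 0.357, or 18.5 points.
- q = 50%, a = 25%: 0.143 vs 0.308, or 16.5 points.
- q = a = 25%: 0.200 vs 0.400, unchanged at 20 points.

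*Women involved.* Expected deletions of symptomatic women are 25pq. At 20% vs 40% this is 1.25 vs 2.5 women for q = 25%, and 2.5 vs 5 for q = 50%.

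*Sampling error.* At 20% vs 40% the standard error of the difference is √(0.16/25 + 0.24/25) = 12.6 points at 25 per arm and 14.1 at 20 per arm.

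**Hemoglobin.** Assume women who stop pills end 0.5 to 1.0 units lower. Using the 20% and 40% symptom rates, the arms lose 0.20q and 0.40q of their women, so deletion shifts the between-arm difference by (0.40q − 0.20q) × 0.5 to 1.0. For q from 10% to 75% this runs from 0.20 × 0.10 × 0.5 = 0.01 to 0.20 × 0.75 × 1.0 = 0.15 units. The standard error is √(2/20) = 0.32 at 20 per arm.

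**The case against.** **The causal link is inferred.** Nothing in the protocol says that symptoms cause missed pills or that missed pills lead to withdrawal. Symptoms are called mild, and significant ones rare. Both arms take an active morning pill from identical blinded packs. This stands as a limit: the point is that withdrawal can depend on the outcome, not that it will. Blinding restrains removal by arm on the investigator's side, but not non-compliance caused by symptoms.

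**The illustrated shifts are small against chance.** At 20% vs 40% the largest shift, from 20 to 8.4 points, is 11.6 points and below one standard error. That is true and tempers the figures. It does not excuse a bias that is built into the plan and cannot be examined afterwards.

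**The rates may not match the plan's GI target.** Power Analysis says 10 women per arm suffice. At 20% vs 40%, Fisher's exact test has only about 6% power at 10 per arm and 23% at 25, so a larger contrast was presumably in mind. At an assumed 20% vs 80%, equal deletion of 25% or 50% of symptomatic women moves 60 points only to 59.2 or 55.6. This is fair. The basis of the 10 is not in the documents, so neither scale is established.

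**Counts might be recovered.** With counts from the pharmacy list, worst-case bounds would remain possible. They could not distinguish the cases above, because the scores would be gone.

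**Conclusion.** The concern holds and must be fixed. Followed as written, the plan removes randomised women on a post-randomisation criterion that can plausibly depend on the GI primary outcome. It then destroys the evidence needed to judge the effect.

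Confidence is high about the rule and its irreversibility. The size and direction of the GI bias are unknown. Under the assumed rates, a true 20-point difference could appear as anything from 8.4 to 23.8 points, or be unchanged if symptomatic and asymptomatic women are withdrawn equally often within each arm. These figures assume a yes/no GI measure that the protocol does not define. A hemoglobin bias is possible but probably small: 0.01 to 0.15 units under the stated assumptions. The case for change rests on the avoidable, permanent loss of randomised data, not on any one scenario.

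**What to change.** Replace the answers on destruction, replacement and follow-up with wording such as:

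> Data already collected are kept, subject to the terms of consent. Unless consent is withdrawn, hemoglobin at admission and on post-partum day 1, transfusion and GI questionnaires are recorded for every randomised woman, whether or not she is taking study pills. Primary analyses include all randomised women in their assigned arm; a compliers-only analysis is supportive. Withdrawals and reasons are reported by arm. The GI comparison is repeated under a range of assumptions about missing scores that differ by arm, on the scale used for that outcome. New recruits do not substitute for randomised women, and all randomised women count toward the 50.

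State as well how missing hemoglobin values will be handled, since the plan expects some loss. Bring the replacement answer and the Power Analysis paragraph into line. None of this touches when pills are stopped.

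**Cost.** The change needs protocol wording, an IRB amendment and possibly revised consent text, which was not available to check. Both hemoglobin values are standard care and study data are already kept for 7 years, so retention adds little. Reaching women who miss visits for questionnaires takes effort; the RedCap option may help.

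Including non-adherent women may dilute the hemoglobin effect. Power (two-sided 0.05 t-test, SD 1, dilution assumed) would be:

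| Retained per arm | Difference 1.0 | 0.9 | 0.8 |
|---|---|---|---|
| 25 (no loss) | 93.4% | 87.7% | 79.1% |
| 20 (20% loss) | 86.9% | 79.2% | 69.3% |
| 17 (32% loss) | 80.7% | 72.1% | 61.9% |
| 15 (40% loss) | 75.3% | 66.3% | 56.2% |

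The 20% row holds if that figure covers all missing women. Power Analysis can also be read as 20% on top of deliveries elsewhere and transfers; the 32% and 40% rows are assumptions for that reading (25 × 0.68 = 17; 25 × 0.60 = 15).

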This will be a prospective, randomized, double blinded placebo controlled clinical trial. Subjects will be identified for possible enrollment during the second trimester during routine prenatal care. Criteria for enrollment will be a singleton intrauterine gestation as above. Subjects without anemia will have weekly questionnaires regarding GI symptoms during otherwise scheduled prenatal visits. Subjects with iron deficiency anemia as diagnosed by an Hgb concentration of less than 10.5-11mg/dL per ACOG guidelines and a ferritin of less than 15mg/dL will be randomized to once or twice daily iron supplementation by means of a computer generated random number list by the investigational drug pharmacy. The study drug will be provided by the University of Missouri Investigational Drug Pharmacy under the guidance of [name], the Investigational Drug Pharmacist for the University. Iron supplementation will be in the form of ferrous sulfate 325mg (65mg of elemental iron) once or twice daily. Anemic subjects will receive identical packs of drug with instructions to take one pill BID (twice daily). The morning pill will be ferrous sulfate 325mg. The evening pill will be randomized to contain either ferrous sulfate 325mg or placebo. The placebo will be produced by the investigational drug pharmacy and contain cellulose, a biologically inert plant fiber. The subjects and investigators will be blinded to assignment. As part of standard Obstetric care, the subject will have a hemoglobin repeated at the time of admission to labor and delivery and on post-partum day 1. Subjects who are not anemic will serve as controls and not receive a prescription. This is appropriate as the standard of care is not to treat non-anemic women with iron supplementation.

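### Withdrawing non-compliant randomised women, destroying their data and replacing them can bias the once- versus twice-daily comparisons, by an amount and in a direction the documents cannot fix

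*Combined protocol and SAP*

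**What the plan says.** All references are to the combined protocol and SAP.

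- **When a woman is withdrawn** (Subject withdrawal criteria and procedures): "If subjects are not compliant with the tasks required in the protocol". No threshold is given, and the tasks are not listed. Study Design instructs anemic women to take a pill twice a day and says that pill packs are checked at visits.
- **What then happens** (same section): "All data collected from a withdrawn subject will immediately be destroyed"; "To replace withdrawn subjects, we will recruit another pregnant mother"; and, on later follow-up, "There will be no follow-up".
- **What differs between the arms** (Study Design): "The evening pill will be randomized to contain either ferrous sulfate 325mg or placebo". The morning pill is iron in both arms. Subjects and investigators are blinded.
- **Dose and symptoms** (Risks and Benefits): "Increased iron dosage may be associated with an increased risk of these symptoms". The same paragraph calls the symptoms mild and significant ones rare at either dose.
- **Primary outcomes** (Summary): "The primary outcomes will be hemoglobin concentration at the time of admission for delivery and post-partum and assessment of gastrointestinal side effects".
- **Routine hemoglobin** (Study Design): as standard care, "the subject will have a hemoglobin repeated at the time of admission to labor and delivery and on post-partum day 1".

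Nothing elsewhere overrides the withdrawal rule. The seven-year retention under Data handling is general and does not mention withdrawn women. Data Analysis names no analysis set and no method for missing data.

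**The concern.** Randomisation makes the two iron groups comparable at the start. Removing women afterwards keeps them comparable only if the removal is unrelated to treatment and outcome, and that cannot be assumed here. If the second iron pill upsets some women and they skip pills, a consequence of treatment becomes the ground for removal. The GI questionnaires recording those symptoms are then destroyed, although GI side effects are a primary outcome. Hemoglobin can be affected too, because women who take their pills poorly may end with different values from those who take them well.

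Two things are at stake. The comparison of the women who remain may differ from the comparison of all women randomised. And, because the records are destroyed and the women replaced, the plan leaves little with which to judge how large that difference was.

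**Working it through.** **1. The plan's own figure.** Power Analysis gives SD 1, difference 1, alpha 0.05 (two-sided assumed), 80% power and 17 per arm. A two-sample t test needs 16.7, so 17, with 80.7% power. The figure reproduces. Allowing for 20% loss, 17 / 0.8 = 21.25, so 22 per arm or 44 in total. The plan randomises 50, that is 25 per arm. The sample size is not the problem.

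**2. GI symptoms.** The documents give no rates, so those below are assumed. Let s be the true share of women with symptoms in an arm and q the share of symptomatic women withdrawn, with no other withdrawals. The rate among women left is s(1 − q) / (1 − sq). Take s = 0.40 (twice daily) and 0.20 (once daily), with the same q in both arms.

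| q | Twice daily | Once daily | Risk difference | Risk ratio | Odds ratio |
|---|---|---|---|---|---|
| 0 | 40.0% | 20.0% | 20.0 points | 2.00 | 2.67 |
| 0.25 | 0.30/0.90 = 33.3% | 0.15/0.95 = 15.8% | 17.5 points | 2.11 | 2.67 |
| 0.50 | 0.20/0.80 = 25.0% | 0.10/0.90 = 11.1% | 13.9 points | 2.25 | 2.67 |

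Both observed rates fall. The risk difference shrinks and the risk ratio grows. The odds ratio does not move, because the odds in each arm become s(1 − q)/(1 − s) and the factor (1 − q) cancels. It cancels only while q is the same in both arms. If true rates and q are equal in the two arms, the observed difference is zero, as it should be.

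**3. Hemoglobin.** Let p be the share withdrawn in an arm and d how far withdrawn women fall below retained women. The retained mean exceeds the mean of all randomised women by p × d. The bias in twice daily minus once daily is therefore p(twice) × d(twice) − p(once) × d(once). Assume 20% v 5% withdrawn and the same gap in both arms:

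- gap 0.5: 0.20 × 0.5 − 0.05 × 0.5 = 0.075
- gap 1: 0.20 × 1 − 0.05 × 1 = 0.15

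That is 7.5% to 15% of the planned difference of 1. With equal shares and equal gaps the bias is zero. If the larger share is withdrawn from the once-daily arm, or the gap is reversed, the sign changes.

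**4. What could still be checked under the rule.** GI questionnaires exist only as study data and would be lost. Admission and post-partum hemoglobin are also clinical values, so they exist outside the study, but the plan makes no provision for using them for withdrawn women.

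**The case against.** The strongest reply is that the route from symptoms to withdrawal is inferred. The rule speaks of tasks in general. Missed visits, questionnaires or blood draws would fit it too, and stopping for intolerance is not named. The protocol also expects mild symptoms, which sits poorly with withdrawing half of all symptomatic women. This limits the likely size. It does not remove the problem: taking the pills is plainly a task, packs are checked, and with no threshold even mild symptoms that lead to missed pills could trigger withdrawal.

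Blinding stops staff from withdrawing women knowingly by arm. It does not stop tolerance from differing by arm. The margin from 17 to 25 per arm protects power, not comparability.

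Three stronger readings are tempting, and the documents do not support them:

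- **That both primary comparisons shift in favour of twice daily.** The table shows that for GI symptoms the direction depends on the effect measure, and the plan names none, nor says that the questionnaire is scored yes/no. For hemoglobin it depends on who is withdrawn. The trial's own hypothesis is that the second dose does not help, so the gap could be nil or reversed.
- **That the false-positive rate rises to between 5.6% and 9.5%.** Such figures follow from assumed biases of 0.075 to 0.20 in a two-sample t test with 20 per arm, whereas the plan specifies a three-group ANOVA. The upper end needs 20% withdrawn in each arm with a gap of 1 in the twice-daily arm alone (0.20 × 1 − 0 = 0.20). A gap confined to that arm is hard to square with an evening pill that has no effect.
- **That everything is lost beyond recovery.** Hemoglobin remains in the clinical record, though using it may need permission that the documents do not address. The pharmacy generates the allocation list, so the number withdrawn by arm may be recoverable. The irreversible loss is clearest for the GI questionnaires.

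**Conclusion.** The point stands as a design weakness: the rule excludes randomised women for a reason that can depend on treatment and on a primary outcome, and so can bias both the GI and the hemoglobin comparison. Neither size nor direction can be established from the documents. Under the assumed rates the hemoglobin bias is modest, 0.075 to 0.15 against a planned difference of 1. The GI risk difference loses 2.5 to 6.1 of its 20 points, while the ratio measures stay the same or rise. If few women are withdrawn, or withdrawn women are alike in both arms, the bias may be negligible, but for GI symptoms the plan discards the evidence that would show it. The rule should be amended before any data are destroyed. It does not by itself invalidate the trial.

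**What to change.** Rewrite the withdrawal section so that stopping study pills is separate from leaving the study:

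- A woman with poor adherence may stop pills but stays in follow-up. Keep all data already collected.
- Collect her routine admission and post-partum day 1 hemoglobin and her GI questionnaires, and analyse her in her randomised arm.
- Only withdrawal of consent ends data collection. Data already collected are kept as the consent allows.
- Do not replace randomised women for non-compliance. Count them among the 50.
- Report by arm how many stop pills, with reasons.

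Separate counts of morning and evening pills and a record of non-study iron would be useful, but are optional.

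**Cost.** An amended section and slightly more data entry, with no new visit or blood draw. Keeping poorly adherent women may dilute the contrast. The table gives two-sample t test power (two-sided 0.05, SD 1) for a planned difference of 1, assuming that the contrast shrinks in proportion.

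| Contrast lost | 20 per arm (25 × 0.8) | 25 per arm |
|---|---|---|
| None | 87% | 93% |
| 10% | 79% | 88% |
| 20% | 69% | 79% |

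This is a price of the as-randomised analysis, not a harm of the present plan. Randomising 25 per arm against the 17 required absorbs part of it.

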Project Title: Once Daily versus Twice Daily Iron Supplementation to Treat Anemia in Pregnancy: A Prospective, Randomized, Placebo Controlled, Double Blinded, Clinical Trial

IRB#: 2004638

Version 8, September 24, 2019

Principle Investigator:

[name]

Assistant Professor, Department of Obstetrics and Gynecology
[name]

Summary

Anemia is a common problem in pregnancy, affecting as many as 1/4 of pregnancies in the developed world in the absence of iron supplementation. It is defined as a maternal hemoglobin (Hgb) less than 11mg/dL in the 1st or 3rd trimester and Hgb less than 10.5mg/dL in the 2nd trimester [1].. Anemia is associated with low birth weight, preterm birth, and increased risk for transfusion at the time of delivery [1]. The most common cause of anemia in pregnancy is iron deficiency. Iron deficiency anemia in pregnancy is typically treated with oral iron supplementation in the form of once or twice daily ferrous sulfate, which contains 65mg of elemental iron.

Iron balance is complex, and iron demands are increased in pregnancy. The fetus, placenta, and increased maternal red blood cell volume require about 1g of additional iron during the entire pregnancy. The average American diet contains only about 15mg of elemental iron, which is insufficient to meet this need[1]. It is recommended that pregnant women consume about double this amount during pregnancy[1].

The absorption of oral iron is low, ranging from 2-28%. Taking iron without food increases absorption. Hepcidin is a key regulator of iron absorption in mammals, increasing hepcidin decreases iron absorption. Hepcidin is increased with morning fasting dosing, which may affect the efficacy of twice daily dosing (Morretti). Well-designed clinical trials describing the optimal dosing for iron to treat anemia in pregnancy are limited [2, 3].

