2. Determine whether once daily dosing of ferrous sulfate 325mg has a lower side effect profile than twice daily dosing.
3. Determine the relationship between frequency of maternal iron administration and maternal hepcidin
4. Determine the relationship between frequency of maternal iron administration and fetal iron stores

Secondary Aim

Determine whether once daily dosing of ferrous sulfate 325mg is associated with a lower rate of maternal blood transfusion at the time of delivery than twice daily dosing.

Inclusion Criteria

Singleton gestation in the second trimester (14-28 weeks) who is not on iron therapy and has a normal hemoglobin electrophoresis if from a high risk group for hemoglobinopathy.

Exclusion Criteria

Multiple gestation, maternal hemoglobinopathy or hemochromatosis, subjects with irritable bowel disease or irritable bowel syndrome, history of bariatric surgery or extensive bowel surgery, or individuals already receiving iron supplementation aside from prenatal vitamins.

Study Design

[figure not shown]

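### The only test named for mean hemoglobin is a three-arm ANOVA that includes about 200 non-randomised controls; no once-versus-twice-daily test is stated for the primary comparison

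*Combined protocol and SAP*

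**What the plan says.** All references are to the combined protocol and SAP.

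- **The question.** The title is "Once Daily versus Twice Daily Iron Supplementation to Treat Anemia in Pregnancy". Aim 1 under Specific Aims is: "Determine whether once daily dosing of oral iron is more effective in raising maternal Hgb concentration than twice daily dosing".
- **The outcome.** The Summary states: "The primary outcomes will be hemoglobin concentration at the time of admission for delivery and post-partum and assessment of gastrointestinal side effects".
- **The design.** Under Study Design, women with iron deficiency anemia "will be randomized to once or twice daily iron supplementation by means of a computer generated random number list". The third group is different in kind: "Subjects who are not anemic will serve as controls and not receive a prescription". The Power Analysis expects 50 randomised women, split equally, and about 200 controls.
- **The analysis.** For mean hemoglobin, the Statistical Analysis paragraph says "ANOVA will be used to assess the difference in mean hemoglobin at the time of admission and post-partum in the three arms". It names no planned contrast, pairwise test or post-hoc procedure. It adds: "Regression analysis will be used to explore the relationships of iron supplementation on maternal hemoglobin at delivery", adjusting for ferritin and hepcidin at enrollment.
- **The sample size.** The Power Analysis gives 17 per arm for 80% power at alpha 0.05, to detect a difference of 1 with an SD of about 1. It does not name the test.

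**The concern.** The omnibus F tests whether all three means are equal. Aim 1 asks whether two of them differ. The third group was selected for not being anemic, was not randomised, and makes up about 200 of 250 women, so a significant F may show only that controls differ from treated women. That would be a correct rejection of the three-group null and would say nothing about dosing.

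Two things are at stake. F might be reported as the dosing result. Or, once the data are in, someone must choose how to extract once versus twice, and that choice changes both the false-positive rate and the power. The randomised comparison is the reason for the trial, so its test should be fixed in advance.

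**Working it through.** **Inputs from the Power Analysis.** Difference 1, SD 1, alpha 0.05, 17 per arm; 25 + 25 randomised and about 200 controls; 20% loss. The SD is given for hemoglobin in pregnancy generally, so using it for treated women is an assumption.

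**Further assumptions.** Completers are 25/25/200 (no loss) or 20/20/160 (20% loss in every group). The documents give neither the control-minus-treated gap at delivery nor a separate control SD, so both are shown as ranges.

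**1. The plan's own sample size.** For a two-sided two-sample t-test, the noncentrality is 1/√(2/n) = √(n/2) on 2n − 2 degrees of freedom.

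| n per arm | noncentrality | critical t | power |
|---|---|---|---|
| 16 | 2.828 | 2.042 | 78.1% |
| 17 | 2.915 | 2.037 | 80.7% |
| 20 | 3.162 | 2.024 | 86.9% |
| 25 | 3.536 | 2.011 | 93.4% |

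So 17 is the two-group t-test size. An equal-size three-group F over a range of 1 would need 21 per arm with the third mean midway, or 16 with it at one extreme. The sizing therefore matches a two-group test that the analysis paragraph does not name.

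**2. The three-arm F when once = twice.** With means (0, 0, gap) and SD 1 throughout, the noncentrality is λ = (n_treated × n_control / N) × gap².

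- 20/20/160: λ = (40 × 160/200) × gap² = 32 gap²; critical F(2, 197) = 3.04.
- 25/25/200: λ = (50 × 200/250) × gap² = 40 gap²; critical F(2, 247) = 3.03.

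| Assumed gap | λ, 20/20/160 | P(F significant) | λ, 25/25/200 | P(F significant) |
|---|---|---|---|---|
| 0 | 0 | 5% | 0 | 5% |
| 0.25 | 2.0 | 22% | 2.5 | 27% |
| 0.5 | 8.0 | 71% | 10.0 | 81% |
| 0.75 | 18.0 | 97% | 22.5 | 99% |

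**3. What an unstated follow-up test would do.** Once versus twice at 20/20/160 with SD 1 in all groups. The gated row is simulated over control gaps from 0 to 1.

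| Follow-up | False positives | Power, difference 1 |
|---|---|---|
| Two-group t-test | 5.0% | 86.9% |
| Contrast, error pooled over three groups | 5.0% | 88.2% |
| Same contrast, made only after a significant F | about 2.5-5% | 80-88% |
| Tukey | 1.9% | 78.8% |

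**4. Dependence on the control SD.** The pooled error variance is (38 × 1² + 159 × SD_control²)/197.

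- Control SD 0.8: (38 + 101.76)/197 = 0.709, root 0.842. The nominal critical value 1.972 becomes 1.972 × 0.842 = 1.66 true standard errors, or about 9.7% false positives by the normal approximation. Simulation gives about 9.8%.
- Control SD 1.2: (38 + 228.96)/197 = 1.355, root 1.164, giving 1.972 × 1.164 = 2.30 and about 2.2%. Simulation gives 2.3%, with contrast power 80.7%.

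The two-group t-test uses no control data, so it stays at 5.0% and 86.9% whatever the control SD.

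**The case against.** The strongest reply is that the comparison is clear and the plan already has ways to reach it. The title, aims and sample size all point to once versus twice. The regression could be coded that way, since the aims on hepcidin and fetal iron treat dosing frequency as the exposure. The Power Analysis mentions controlling for covariates alongside the primary outcomes, which suggests that adjustment belongs to the main analysis. And the ordinary step after ANOVA, a pairwise contrast if F is significant, performs about as intended at the plan's single SD and 20% loss.

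Much of this stands, and it rules out several stronger readings.

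- A reader might infer that the plan never tests its primary aim, or that the regression is labelled exploratory. The text only uses the verb explore, and a once-versus-twice coding for delivery hemoglobin is possible. But no population or coding is stated and post-partum hemoglobin is not covered, so the regression does not supply the primary test.
- A reader might take 71-81% as a false-positive rate for dosing. It is the chance of correctly rejecting the three-group null, and misleads only if F is read as once versus twice.
- A reader might conclude that power is inadequate. The two-group calculation reproduces and is met at 17 per arm.

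The pairwise step after F is not written down either, and it shares the dependence on the control SD. Tukey is likewise not in the documents; it is used here only to show that the choice matters.

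**Conclusion.** The concern holds as an under-specified primary test. The one test named for mean hemoglobin does not by itself answer aim 1, and nothing else in the plan fixes the once-versus-twice test at both time points.

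An F driven wholly by controls would be common at modest gaps. That result rests on SD 1 in all groups and on assumed gaps, though controls chosen as non-anemic make some gap plausible. The spread between follow-up tests at 20/20/160 is smaller but real: 1.9% to 5.0% false positives and 78.8% to 88.2% power with equal SDs, and up to about 9.8% false positives for the pooled contrast if the control SD were 0.8. The 0.8 is an assumption.

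This should be corrected before analysis because it concerns the primary randomised comparison. The design, the data collected and the sample size all support the right test.

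**What to change.** In the Statistical Analysis paragraph:

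1. Name as the primary hemoglobin analysis, at admission and post-partum, the once-minus-twice-daily difference in means among randomised women only, with a 95% CI and two-sided alpha 0.05.
2. Choose one method in advance: a two-sample t-test, or a regression/ANCOVA restricted to randomised women with the enrollment covariates the plan already intends. Either is valid. If the regression is chosen, state its population and arm coding and extend it to post-partum hemoglobin.
3. Do not pool the error variance with the controls.
4. Keep the three-arm ANOVA as secondary and label it a non-randomised comparison.

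The secondary aim already sets transfusion as once versus twice ("is associated with a lower rate of maternal blood transfusion at the time of delivery than twice daily dosing"), so naming the randomised women there would only write down what is intended. Multiplicity over the two hemoglobin time points is a separate matter that this wording does not settle.

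The cost is wording only. With the t-test, power is 93.4% at 25 per arm, 86.9% at 20 and 80.7% at 17. Falling from 25 to 17 would be a loss of 8/25 = 32%, against the planned 20%. The plan also lists delivery elsewhere and transfer of care, but it replaces withdrawn women.
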